Predictability of OSA with a Subjective Screening Scale

Predictive Value of OSA Based on the Evaluation of the Subjective Feeling of the Air Flow Through Airways, a Randomized Controlled Study

About the study protocol:

The oropharynx, due to its specific layout in humans, is unstable under the effect of inspiratory depression during ventilation. Continuous control of the oropharyngeal lumen is necessary to ensure optimal ventilation.

The combined role of all the pharyngeal dilator muscles and the muscles constituting the pharyngeal groove is essential for maintaining the patency of the pharyngeal upper airway. The action of these muscles allows for the postural adjustment of the pharyngeal cavities and the rigidity of the entire pharyngeal muscular groove.

The permeability of the upper airways is therefore largely dependent on optimal tone of the muscles constituting the walls of the upper airways. The management of the tone of these muscles is possible thanks to the numerous mechanosensory receptors present in the upper airways. There are many of them, among which some are sensitive to changes in shape, the passage of air, variations in temperature, pressure, etc. The opening reflex of the upper airways depends on the integrity and quality of these receptors. Several known factors can lead to an alteration of these receptors: vibrations of the soft palate, edema, inflammation, hypoxia, GERD, drying of the mucous membranes, postnasal drip, etc.

In sleep disorders, the excitability threshold of these receptors can vary depending on the extent of VAS resistance (SRAVAS), or even collapse (OSA). It is possible that the sensitivity of these receptors is exacerbated in cases of SRAVAS and mild OSA and reduced or even inhibited in severe forms of OSA.

Numerous parietal factors modify the volume and permeability of the pharynx (pharyngeal lumen) and act through different mechanisms:

- Modification of the pharyngeal lumen in the transverse and sagittal dimensions
- Modification of transmural parietal tension (longitudinal tension) and therefore of the compliance of the pharyngeal wall by the passive and active tension of the pharyngeal muscles (tonic, phasic)

Considering the permeability of the pharynx, we can identify biomechanical parameters that increase resistance to the passage of air in the upper airways (aggravating parameters) and others that decrease resistance (facilitating parameters).

Aggravating factors:

- Supine position
- Altered state of consciousness (first sleep stage)
- Mouth breathing and loss of lingual-palatal and labial-labial contact
- Passive craniocervical flexion

Facilitating parameters:

- Cephalocervical extension
- Mandibular advancement
- Tongue protraction
- Efficient nasal ventilation

These considerations allow us to establish an examination protocol to attempt to answer the following questions:

- Can the subject consciously perceive variations in airflow/or intraluminal pressure in the upper airways caused by the various aggravating and facilitating parameters?
- Can the sensations of ventilatory flow/intraluminal pressure felt by the subject constitute a complementary tool for screening for obstructive sleep disorders?

The goal of the clinical examination is to cause instability of the oropharyngeal mechanics. This instability can cause a modification of the pharyngeal lumen and a modification of the resistance of the VAS to the pressure linked to the ventilatory flow. These will lead to a modification of the inspiratory pressure gradient and stimulate the mechanoreceptors located in the VAS. The responses to a questionnaire by subjects who present sleep disorders exposed to these variations in resistance (aggravating or facilitating) on their subjective feeling allows the establishment of a perception scale which, compared to a control group without sleep disorders, will determine if the sensitivity of the inputs is comparable between the groups and if a tool for screening sensory inputs is possible.

Protocol:

The questionnaires to assess patients' pharyngeal ventilatory perceptual potential/the quality of spontaneous nasopharyngeal perception during ventilation are administered when patients come to the consultation to request the results of the pharyngeal ventilatory perceptual analysis. The examiners are blinded, unaware of the results. Patients are randomly assigned according to their order of arrival. The first questionnaire consists of 7 items selected to aggravate or facilitate upper airways permeability (supine position, modified state of consciousness with muscle relaxation, tongue posture, cephalic flexion, cephalic extension, mandibular protraction, nostrils aperture). This first questionnaire try to evaluate if all subjects are able to feel aggravating or facilitating factors by on/off answers. The second questionnaire consists of 18 items related to upper airway collapsibility. Each item concerns the aggravating or facilitating factors perceived by the patient or the therapist with clinical maneuvers, factors known to be unfavourable to the permeability of the upper airways (snoring, oral ventilation, tonsils, dento-skeletal class, etc.), as well as two questionnaires used in the sleep laboratory of the André Renard clinic (Epworth Sleepiness Scale and FFF questionnaire).

[figure not shown]
For each of these items, the patient's or practitioner's response will be noted.

Performing the examination:

- Sensory-motor awareness of nasal and pharyngeal breathing (patient in a seated position): explain to the patient what to observe and feel and where (soft palate, tonsils, vibration during snoring, etc.)
- Read the questionnaire to the patient: it must be understood
- Ask the patient to answer each item and record the response.

The examination lasts approximately 20 minutes.

This examination requires patient involvement but carries no risks or side effects.

STATISTICAL ANALYSIS PLAN

(translation of the Statistical analysis report download in SAP section from an independent Biostatistician: [name], MyStat.be)

Software used for analysis: R version 4.4.1(R Core Team (2024). R: A language and environment for statistical computing. R Foundation for Statistical Computing, Vienna, Austria. URL <https://www.R-project.org/>) and Microsoft Excel for manipulating and preparing the data tables. data files used and appended: d1_final.csv, d2_final.csv

1 - d1_final.csv: sensitivity parameters taken from 112 patients

2 - d2_final.csv: parameters taken from 101 patients (excluding CHR patients considered normal after polysomnography)

Discrete variables for classification into groups :

- STATUS3: 2 categories: healthy patients (= non-CHR control patients and normal CHR patients) and pathological patients (= CHR patients affected to varying degrees)
- STATUS4: 4 categories: control patients (= non CHR), normal patients (= CHR N), mild symptom patients (= CHR SL), moderate symptom patients (= CHR SM) and severe symptom patients (= CHR SS).

A. Descriptive statistics (based on file n°1 - sensitivity)

B. Descriptive statistics (based on file n° 2 - predictive score)

C. Normality tests for intermediate and final scores

- Parameter ST1 (SubTotal1) = aggravating parameters

Shapiro-Wilk normality test

- Parameter ST2 (SubTotal2) = facilitating parameters

Shapiro-Wilk normality test

- Parameter ST1+ST2 (SubTotal1+ SubTotal2) = subjective sensitivity of patients

Shapiro-Wilk normality test

- Parameter ISF (Intermediate Final Score) = subjective sensitivity of patients and practitioner

Shapiro-Wilk normality test

- Parameter TFS (Total Final Score) = subjective sensitivity of patients and practitioner + valuable factors

Shapiro-Wilk normality test

D. Spearman correlation tests between final scores and certain variables

E. Non-parametric tests on patient sensitivity :

Given the non-normal distribution of the various variables other than IFS and TFS, non-parametric tests (based on the median of the data) were applied to analyse the differences between the groups (according to the STATUS3 and STATUS4 classification criteria). To analyse any differences in sensitivity between patient groups, Kruskal-Wallis tests were applied. In this type of analysis, having a p-value greater than 1% and ideally greater than 5% would indicate the absence of differences between groups.

Then, to see if the median of a particular group is different from 0 (= no sensitivity: not feeling the differences in airflow induced by the different tests given by the operator), Wilcoxon tests were performed on each group of data. If the p-value is small (less than 5%, ideally less than 1%), the null hypothesis that the score is identical to 0 is rejected. In this case, it means that the patients in the test group feel the differences in airflow depending on their position. This is the case for all the patient groups tested on ST1, ST2 and ST1+ST2.

[figure not shown]
F. Parametric tests on the prediction of patients' pathological status (SFI and SFT scores):

For these analyses, as the IFS and TFS scores follow a normal distribution, ANOVAs (analyses of variance) were performed. For discrete variables with more than 2 levels of value (STATUS4), a post-hoc 2-to-2 comparison analysis was performed (Tukey) to see which level of the variable differed from one another. Significant values are highlighted in bold red.

[figure not shown]
G. Determination of cut-off values for IFS and TFS:

[figure not shown]
The Cutoff_final txt file includes the various sensitivity and specificity calculations as well as the Youden index in order to determine the best cut-off value (largest Youden). The ROC curves allow the values in the file to be appreciated graphically.

Upper rhino-oro-pharyngeal airway permeability - Subjective neuro-sensory evaluation

Assessment of oro-pharyngeal sensitivity				
Date :	Name:			age:
Tests	Items			Score 1 0
	Aggravation or facilitation felt = 1 No aggravation or no facilitation felt = 0			
Aggravation maneuver	1	Supine position		
Aggravation maneuver	2	Modified state of consciousness (overall relaxation)		
Aggravation maneuver	3	Cephalic Flexion		
Aggravation or Facilitation maneuver	4	Upper-anterior tongue to lower tongue (= aggravation) or lower tongue to upper-anterior tongue (= facilitation)		
Facilitation maneuver	5	Cephalic Extension		
Facilitation maneuver	6	Mandibular protrusion		
Facilitation maneuver	7	Nostrils aperture		
Total Score				... / 7
Comments :				
www.osteovox.be				

Upper rhino-oro-pharyngeal airway permeability - Subjective neuro-sensory evaluation						
Date :	Name :			age: IMC:		
Tests	Items			Scores		
	0	0,5	1	2		
Aggravation maneuver	1	Supine position: aggravation=1 / no aggravation= 0				
Aggravation maneuver	2	Modified state of consciousness (overall relaxation) aggravation=1 / no aggravation= 0				
Aggravation maneuver	3	Cephalic flexion: aggravation at the start of flexion ($\leq 6^\circ$)=2 / in the middle of flexion ($7\text{--}>10^\circ$)=1 / at the end of flexion ($\geq 11^\circ$)=0				
Facilitation maneuver	4	Cephalic extension: facilitation from the start of extension ($\leq 6^\circ$)=2 / in the middle of extension ($7\text{--}>10^\circ$)=1 / at the end of extension ($\geq 11^\circ$)=0				
Facilitation maneuver	5	Measurement of range: amplitude between cephalic flexion and extension: reduced ($\leq 12^\circ$)=2 / medium ($13\text{--}>20^\circ$)=1 / large ($\geq 21^\circ$)=0				
Facilitation maneuver	6	Mandibular advancement: Physiological=2 / Tooth butt =1 / Anterior crossing=0.5 / no facilitation= 0				
Therapist observation	7	Therapist palpation of the contraction of the buccal floor on inspiration at rest yes=2 / no=0				
Therapist observation	8	Sound perception of ventilation by the therapist: yes=1 / no=0				
Intermediate Final Score (IFS): low risk of OSA ≤ 7.5 / risk of OSA ≥ 8				... / 13		
Aggravated situation	9	Low lingual posture in supine position : yes=2 / no=0				
Subjective perception of nasal permeability	10	Do you regularly have difficulty breathing through your nose? yes=1 / no= 0				
Subjective perception of snoring	11	Do you snore at night? yes=1 / no=0				
Subjective perception of daytime ventilation patterns	12	During the day, you breathe mainly: through the mouth=1 / mixed nose-mouth=0,5 / through the nose =0				
subjective perception of nocturnal breathing patterns	13	At night, you breathe mainly: through the mouth=2 / mixed nose-mouth=1 / through the nose =0				
Therapist observation	14	Dento-skeletal class: class I or III = 0 / class II = 1				
Therapist observation: Tonsils: grades 0-1-2 =0 / grades 3-4 =1	15	Quote : 				
Therapist observation: Mallampati: grade 1-2 =0 / grade 3-4 =1	16	Quote : 				
Epworth Sleepiness Scale	17	score: ≤ 8 =0 / $9\text{--}>14$ =1 / ≥ 15 =2				
FFF questionnaire	18	score ≤ 10 =0 / ≥ 11 =1				
Final Total Score (FTS): low risk of OSAS ≤ 10 / high risk of OSAS ≥ 11				... / 26		
Comments :						
www.osteovox.be						

Study process adapted from the CONSORT 2010 flowchart.

STUDY GROUP: The final sample included 41 patients diagnosed with OSAH (mild= 9, moderate=18; severe= 14).

The study sample included 13 women and 28 men, with a mean age of 49.30 years, and a mean body mass index (BMI) of 30.70 kg/m².

CONTROL GROUP: The final sample included 60 patients without OSA based on subjective scales used in sleep medicine in Liège (Epworth, Berlin, Pichot, FFF).

The study sample comprised 20 men and 40 women, with a mean age of 41.76 years and a mean body mass index (BMI) of 22.78 kg/m².

Predictability of OSA with a Subjective Screening Scale

Predictive Value of OSA Based on the Evaluation of the Subjective Feeling of the Air Flow
Through Airways, a Randomized Controlled Study

Herstal, February 3, 2023

Favorable Opinion

Composition of the Ethics Committee:

- - [name] - Vascular Surgeon
- - [name] - External General Practitioner
- - [name] - Palliative Care
- - [name] - Anesthesiologist
- - [name] - Geriatrician
- - Maître [name] - Lawyer at the Liège Bar
- - [name] - Hospital Mediator
- - [name] - Psychologist
- - [name] - Social Worker
- - [name] - Hospital Pharmacist
- - [name] - Nurse in the Intensive Care Unit

Subject:

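### In the 101-patient file recruitment source equals class, and the stated examiner blinding does not claim to mask source, so therapist-scored points could carry expectation bias into the IFS and FTS cut-offs.

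*Combined protocol and SAP*

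**What the plan says.** Blinding is covered by one sentence in the Protocol section: "The examiners are blinded, unaware of the results". Next to it stands "Patients are randomly assigned according to their order of arrival". Neither mentions recruitment source.

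The SAP lists two files. The first is "d1_final.csv: sensitivity parameters taken from 112 patients"; the second holds "parameters taken from 101 patients (excluding CHR patients considered normal after polysomnography". The two-level class variable STATUS3 contrasts "healthy patients (= non-CHR control patients and normal CHR patients) and pathological patients (= CHR patients affected to varying degrees". SAP section B labels the second file as the predictive score, and section G derives cut-offs for IFS and the final total score (TFS in the SAP, FTS on the form) by ROC and the Youden index.

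The sample description after the forms says "The final sample included 41 patients diagnosed with OSAH (mild= 9, moderate=18; severe= 14". It gives 60 controls, judged free of OSA on subjective scales.

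The 18-item form labels items 7, 8 and 14-16 as therapist observations. Item 7, for instance, is "Therapist palpation of the contraction of the buccal floor on inspiration at rest", scored 2 or 0.

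**The concern.** Blinding matters here because part of each score is the examiner's own judgement. It protects a case-control contrast only if the examiner cannot infer the class by another route. In the second file the class can be read from where the participant was recruited. Withholding a test result does not remove that cue, and for the controls no polysomnography result is described that could be withheld.

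If source was recognisable, a tendency to score CHR patients higher on palpation or audible breathing would raise IFS and FTS in cases for reasons unrelated to OSA. It would then pass into the ROC curves and cut-offs. A reader who sees the word blinded would take this route to be closed.

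**Working it through.** **1. Does source equal class in the second file?** Inputs: the sample description and the SAP file list.

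- Cases: 9 + 18 + 14 = 41, all CHR by the STATUS3 definition.
- Cases plus controls: 41 + 60 = 101, which reproduces the stated file size exactly.
- No place is left for a CHR non-case or a non-CHR case. Source alone classifies 41/41 cases and 60/60 controls: Youden = 1.00 + 1.00 - 1 = 1.00.

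**2. How strong was the cue at examination?** The normal CHR patients had not yet been removed. If the second file is the first minus those patients, they number 112 - 101 = 11.

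- CHR patients who were cases: 41 / (41 + 11) = 41/52 = 78.8%.
- Participants whose source matched their class: 101/112 = 90.2%.
- Youden of source in the 112: 41/41 + 60/71 - 1 = 0.845.

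The cue was strong but imperfect. The perfect match arises after the exclusion.

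**3. How much of each score is therapist-scored?** Inputs: item maxima on the 18-item form.

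- Items 1-8: 1+1+2+2+2+2+2+1 = 13. Items 9-18: 2+1+1+1+2+1+1+1+2+1 = 13, so 26 in all. Both totals match the form.
- IFS, items 7-8: 2 + 1 = 3 of 13 (23.1%).
- FTS, items 7, 8, 14, 15, 16: 2+1+1+1+1 = 6 of 26 (23.1%).
- Item 7 alone can take an IFS of 6 to 7.5 from the form's low-risk band (7.5 or less) to 8 or more.

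**4. What could a scoring shift do?** The documents give no SD, so this is an illustration. Assume normal scores with equal variance, no true difference, and a mean shift in cases only. Then AUC = Φ(shift / (SD × √2)).

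| Mean shift | How it could arise | SD 2 | SD 3 |
|---|---|---|---|
| 0.3 | items 7 and 8 each wrongly scored yes in 10% of cases: 0.1×2 + 0.1×1 | 0.54 | 0.53 |
| 0.5 | item 7 wrongly scored yes in 25% of cases | 0.57 | 0.55 |
| 1.0 | item 7 wrongly scored yes in 50% of cases | 0.64 | 0.59 |

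The last row is an upper-end case, not a small shift: it uses one third of the therapist points in IFS.

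**5. Precision of a ROC within CHR patients.** Hanley-McNeil with 41 cases, 11 normals and assumed AUC A = 0.75:

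- A/(2-A) = 0.600; 2A²/(1+A) = 0.643; A² = 0.5625.
- Variance = [0.1875 + 40×(0.600-0.5625) + 10×(0.643-0.5625)] / (41×11) = 2.49/451 = 0.0055.
- SE = 0.074, so the 95% CI is about ±1.96×0.074 = ±0.15.

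**The case against.** A reader might infer that the examiners knew who was a CHR patient and that the cut-offs are therefore biased. The documents do not support that. They do not say that source was known; they only fail to say that it was masked. CHR is not expanded and the controls' recruitment setting is not described. The size and direction of any bias cannot be estimated from the text.

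A reader might also take the blinding to mean blinding to polysomnography. The text does not say so, and the preceding sentence refers to results of the perceptual analysis. This uncertainty does not remove the point, since neither reading masks source, but it means that even a comparison within CHR patients is protected only if the polysomnography result was among those withheld.

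Three further objections stand in part:

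- Neither re-analysis isolates expectation bias. Dropping therapist items also removes true signal, and the Protocol section itself counts tonsils and dento-skeletal class among the unfavourable factors. Restricting to CHR patients changes the comparison group: the present controls have a mean BMI of 22.78 kg/m² against 30.70 in cases.
- The SAP describes the 112-patient file as sensitivity parameters, so IFS and FTS may not exist for the normal CHR patients.
- Items 14-16 grade anatomy and are less open to expectation than palpation or sound.

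In the other direction, the examiner also explains what to feel, reads out the questions and records the answers. The labelled therapist points may therefore understate the exposure.

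**Conclusion.** The point holds as a conditional one. The match between source and class is exact (41 + 60 = 101), and the stated blinding does not claim to break it. If examiners could recognise source, up to 3 of 13 IFS points and 6 of 26 FTS points were open to expectation. By itself this could give a useless score an AUC of about 0.54-0.64 at SD 2, or 0.53-0.59 at SD 3, for mean shifts of 0.3 to 1 point.

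This rests on assumed SDs and shifts, and on section G using the second file. Section G names no file, but the second is the one labelled predictive score. The figure of 11 normal CHR patients is inferred by subtraction. What is established is an unprotected route for bias, not that bias occurred.

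**What to change.** In SAP section G:

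1. Report the ROC and Youden cut-off for IFS without items 7-8 (maximum 13 - 3 = 10) and for FTS without items 7-8 (maximum 26 - 3 = 23). Secondarily, report FTS also without items 14-16 (maximum 20). Each reduced score needs its own cut-off. Present this as a test of how far performance depends on examiner judgement: a drop does not prove bias, and an unchanged AUC does not fully clear the items that the examiner reads out and records. It also brings the analysis closer to the protocol's own question, whether sensations felt by the subject can help in screening.
2. If IFS and FTS were recorded for the normal CHR patients, report the ROC within CHR patients only. Note that the comparison group differs and that the 95% CI is about ±0.15 at an AUC of 0.75. If they were not recorded, say so.

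In the Protocol section, state which results the examiners were unaware of and whether recruitment source was masked. If it was not, do not present the case-control cut-offs as protected by blinding.

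The cost is a little extra analysis and a clarifying sentence or two, with no new patients or assessors. The within-CHR estimate will be imprecise, and the reported AUC may come out lower.

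### Section E reads any score above 0 as perception of airflow change, but the coached examination and a form with no neutral item cannot separate perception from prompted agreement

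*Combined protocol and SAP*

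**What the plan says.** The first of the two study questions is "Can the subject consciously perceive variations in airflow/or intraluminal pressure in the upper airways caused by the various aggravating and facilitating parameters". The Protocol section describes what is assessed as "the quality of spontaneous nasopharyngeal perception during ventilation".

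Under Performing the examination, the examiner is to "explain to the patient what to observe and feel and where (soft palate, tonsils, vibration during snoring, etc", and then: "Read the questionnaire to the patient: it must be understood". The patient's answers are recorded after that.

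On the instrument for this question, the Protocol section says "The first questionnaire consists of 7 items selected to aggravate or facilitate upper airways permeability" and "This first questionnaire try to evaluate if all subjects are able to feel aggravating or facilitating factors by on/off answers". The scoring line on the printed form is "Aggravation or facilitation felt = 1 No aggravation or no facilitation felt = 0".

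SAP Section E applies Kruskal-Wallis tests across groups and reads a large p-value as no difference. It then applies Wilcoxon tests of each group against 0, with 0 defined as no sensitivity. On rejection, "it means that the patients in the test group feel the differences in airflow depending on their position". It reports rejection for all groups on ST1, ST2 and ST1+ST2.

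**The concern.** Perception is inferred from a yes given by a patient who has been told what to feel and where, and has had the form read out. Three controls that would distinguish a felt change from agreement with the examiner are missing:

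- No neutral or sham manoeuvre is described.
- No answer counts against the patient. An opposite-direction report has no code of its own, and the lowest possible score is 0.
- No objective airflow measure is described. The examiners' blinding is to results, not to the effect each manoeuvre is expected to have.

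The reference value of 0 makes this worse. A patient who perceives nothing but sometimes agrees has a score above 0, so the Wilcoxon null can be false without any perception. The Kruskal-Wallis test does not help. Prompting that acts equally in all groups also makes the groups look alike, which Section E reads as equal sensitivity.

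At stake is the answer to one of the study's two questions. The coaching also sits badly with the Protocol section's own description of the perception as spontaneous.

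**Working it through.** **Inputs from the documents.** Group sizes: mild 9, moderate 18, severe 14 (9 + 18 + 14 = 41), control 60 (41 + 60 = 101). The sensitivity file has 112 patients, so the patients found normal after polysomnography number 112 − 101 = 11. The first questionnaire has 7 items. The Section E threshold is 5%, ideally 1%; two-sided is assumed. The plan gives no design figure for this question, so there is none to reproduce.

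**Assumptions.** No true perception, a false-yes probability *q* per item (not documented, so shown as a range) and independent items.

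**Step 1: how little the test needs.** With *m* non-zero scores, all positive, the exact two-sided signed-rank p-value is 2/2^m. For m = 5 it is 0.0625; for m = 6 it is 0.031. Six non-zero patients are enough at 5%, whatever the group size.

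**Step 2: patients scoring above 0 by prompting alone.** P(non-zero) = 1 − (1 − q)^k for k items.

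| q | k = 3 | k = 4 | k = 7 |
|---|---|---|---|
| 0.1 | 0.271 | 0.344 | 0.522 |
| 0.2 | 0.488 | 0.590 | 0.790 |
| 0.3 | 0.657 | 0.760 | 0.918 |

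**Step 3: probability of six or more non-zero patients in the smallest group (n = 9).** Binomial tail with the Step 2 probabilities.

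| q | k = 3 | k = 4 | k = 7 |
|---|---|---|---|
| 0.1 | 0.01 | 0.05 | 0.30 |
| 0.2 | 0.23 | 0.46 | 0.90 |
| 0.3 | 0.63 | 0.85 | >0.99 |

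Larger groups reach six more easily. On the 7-item total at q = 0.2 the probability is 0.985 for n = 11 and above 0.99 for n = 14, 18 and 60.

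**Step 4: the full pattern that Section E reports.** The Wilcoxon test was simulated with 1,500 runs per setting, a tie-corrected normal approximation and prompting as the only source of a yes. On the 7-item total, all five groups reject together in 26%, 91% and 99.8% of runs at q = 0.1, 0.2 and 0.3. Rejection on ST1, ST2 and their sum in all five groups, assuming a 3 + 4 item split, occurs in about 0%, 10%, 56% and 99% of runs at q = 0.1, 0.2, 0.3 and 0.5.

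**Step 5: sensitivity to independence.** With mean q = 0.2 and within-patient correlation 0.3 (beta-binomial), P(non-zero) on 7 items falls from 0.790 to 0.541, and the n = 9 probability from 0.90 to 0.34. If 20% of patients say yes to everything and the rest to nothing, the probabilities are 0.003 (n = 9), 0.04 (n = 14) and 0.13 (n = 18).

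**Step 6: what a neutral comparison does.** With 7 neutral trials per patient (an illustrative number) and a paired Wilcoxon test of active minus neutral score, prompting alone at q = 0.1 to 0.5 rejects in about 2.5% to 6% of runs in every group, close to the nominal 5%.

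**The case against.** Several counter-arguments have force.

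*The tested scores may not come from the first form.* This stands. That form prints only a total out of 7, and its item 4 can be either aggravation or facilitation. The SAP's sequence from ST1 and ST2 to the intermediate score fits the second form: items 1–3 (maximum 4), 4–6 (maximum 6) and 7–8 (maximum 3) give 4 + 6 + 3 = 13, the printed maximum. There, flexion, extension and mandibular advancement are graded, and a flexion or extension effect felt only at the end of movement scores 0. The documents do not settle the source. The main point survives either way, because the second form also has no neutral manoeuvre and no negative score.

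*The size depends on an undocumented rate and on independence.* This also stands. A suggestible patient would tend to say yes repeatedly, and Step 5 shows how far that lowers the figures.

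*Some explanation of the task is legitimate, and its examples are sites and snoring vibration rather than easier or harder breathing.* Fair. It is not stated that the column labelling each manoeuvre is read aloud. But the form is read to the patient and its scoring line names the effect. The weakness is explanation without a control condition.

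*Prediction of OSA (Sections F and G) does not need a yes to be true perception.* Correct. This point is confined to Section E.

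A reader might also infer that relief on leaving flexion is recorded as facilitation by extension. The documents do not support this for the first form: the tongue item lies between the two, and nothing says that manoeuvres run in printed order without a reset.

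**Conclusion.** The Section E conclusion that patients feel airflow differences does not follow from the test as designed. Perception and prompted agreement both raise a score that cannot fall below 0, and neither the Wilcoxon nor the Kruskal-Wallis test can tell them apart. This rests on the text alone and needs no value of q.

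The size does depend on q. On a 7-item total with independent answers, a false-yes rate of about 20% would usually be enough for every group to reject without any perception. On 3- to 4-item subtotals the smallest group would often not reject at that rate, and clustering within patients lowers the figures further.

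A reader might infer that prompting produced the reported result, or that patients perceive nothing. The documents support neither. They give no rate of prompted answers, and at 10% or less, under the independent-items model with a 3 + 4 split, prompting alone would almost never give the full reported pattern. What is established is that the two explanations cannot be separated.

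**What to change.** **For the data collected.** Replace the Section E conclusion with a statement that patients report an effect when prompted, and drop the claim that they perceive airflow differences. Read a non-significant Kruskal-Wallis result with the same limit. State which form supplies ST1 and ST2, and which items enter each. This costs only wording.

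**For any further use of the form.** After each manoeuvre, ask whether breathing is easier, harder or unchanged, without naming the expected effect. Include a neutral catch item. Test predicted-direction answers against opposite-direction answers rather than against 0. One catch item per patient estimates the false-yes rate only coarsely, and some patients may still guess the direction. The cost is a revised answer column and one short item in an examination of about 20 minutes, with slightly longer administration and probably lower scores.

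### The section headed as the statistical analysis plan is a report of a completed analysis; no prespecification is shown, so its p-values and cut-offs cannot be presented as planned or confirmatory

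*Combined protocol and SAP*

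**What the plan says.** The note under the heading STATISTICAL ANALYSIS PLAN gives the origin of the text: "translation of the Statistical analysis report download in SAP section from an independent Biostatistician". The same paragraph lists "data files used and appended: d1_final.csv, d2_final.csv". The files are described by realised size: "d1_final.csv: sensitivity parameters taken from 112 patients", and for the second file "parameters taken from 101 patients (excluding CHR patients considered normal after polysomnography".

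Section E adopts non-parametric tests because the scores other than IFS and TFS were not normally distributed. After explaining how a Wilcoxon test against 0 is read, it gives the result: "This is the case for all the patient groups tested on ST1, ST2 and ST1+ST2". Section F justifies the parametric analysis in the same way: "as the IFS and TFS scores follow a normal distribution, ANOVAs (analyses of variance) were performed". Section G says that an existing output file holds the sensitivity, specificity and Youden calculations, and that the largest Youden index gives the best cut-off. The second scoring form prints risk bands for both scores: 7.5 or less against 8 or more for IFS, and 10 or less against 11 or more for the total score (TFS in the SAP, FTS on the form).

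**The concern.** A statistical analysis plan tells the reader which analyses were chosen without knowledge of the outcomes. That is what lets a p-value be read at its nominal level and a cut-off be read as something tested rather than fitted. Here the text under that heading describes completed work, reports a finding and gives observed data features as the reason for its tests.

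The title speaks of predictive value and of a randomized controlled study, and the scoring form sorts people into OSA risk bands. A reader who sees a section labelled as the plan will take the p-values and bands as confirmatory support for a screening tool. If no choice can be shown to precede the data, the material supports only hypothesis generation, and the conclusions need to say so.

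**Working it through.** The point rests mainly on setting the sections side by side, with a little arithmetic.

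1. **Was the final sample known when the text was written?** The study-group paragraph gives 9 mild, 18 moderate and 14 severe patients: 9 + 18 + 14 = 41. The control group is 60, and 41 + 60 = 101, exactly the size of the second file. The two files differ by 112 − 101 = 11, which fits the excluded polysomnography-normal CHR patients, although the document does not state that number. So the text was written with the final sample known.

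2. **How are the tests chosen?** Section C lists Shapiro-Wilk tests for five scores and states no outcome. Sections E and F then take the outcomes as given: non-normal for the scores other than IFS and TFS, normal for those two. A plan would state a condition (if normality is rejected, use one test; otherwise the other). These sections state what was found.

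3. **Are results stated?** Yes. The last sentence of section E's text reports rejection for all groups on ST1, ST2 and their sum. Neither tense nor translation can account for that.

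4. **Is an error level or primary analysis fixed?** Section E works with two levels at once: p above 1% and ideally above 5% for no difference between groups, and below 5% and ideally below 1% for a difference from 0. No analysis is named as primary.

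5. **Does another part of the document fill the gap?** The introductory part poses two questions and a general aim of comparing groups and judging whether a screening tool is possible. The Protocol section covers the questionnaires, blinding, assignment and conduct of the examination. Neither names a test, an alpha, a primary endpoint, an analysis set or a cut-off rule.

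6. **What do the dates add?** The SAP cites "Software used for analysis: R version 4.4.1(R Core Team (2024" and the ethics opinion is dated "Herstal, February 3, 2023". The text is therefore later than the opinion. No data-collection dates are given, so nothing more follows from the dates.

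7. **What could fitting a cut-off in the same sample do?** This is an illustration under assumptions, because the documents give no score distributions. Take normal scores with SD 2.5, rounded to 0.5 points, control mean 9, with 60 controls and 41 patients and 4,000 simulated samples per row. Let J = sensitivity + specificity − 1, choose the cut-off with the largest J, and compare that J with the true J at the same cut-off.

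| Standardised difference | Mean J in the same sample | Mean true J | Overstatement |
|---|---|---|---|
| 0 | 0.099 | 0.000 | 0.099 |
| 0.5 | 0.258 | 0.175 | 0.082 (from unrounded means) |
| 1.0 | 0.428 | 0.361 | 0.067 |
| 1.5 | 0.583 | 0.527 | 0.056 |

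Under these assumptions the overstatement is about 0.06 to 0.10. It applies only if the cut-offs were chosen and judged in this sample.

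**The case against.** The strongest reply is that the date of a text is not the date of a decision. Testing normality and then choosing between parametric and non-parametric methods is a rule that can be fixed in advance, and its outcome can only be reported afterwards. The note discloses the origin of the text openly, the stated aims are tentative, and an earlier dated plan may exist outside these documents.

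Most of this stands, and it limits what can be said. A reader might infer that the files, tests and cut-offs were all chosen after the outcomes were seen. The documents do not show that; they show only that no earlier choice is recorded. A reader might also infer that the printed cut-offs were derived from these 101 patients. Section G makes that the natural reading, but nowhere is it stated.

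A reader might try to size the problem by counting tests and quoting a family-wise error rate. That would measure multiplicity, which would be the same had every test been prespecified. It would also mix in the Kruskal-Wallis tests, where section E hopes for a large p-value. Nor does the remark in section F about highlighting significant values amount to an inferential rule; it describes table formatting.

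The reply does not rescue the label. A plan that may exist elsewhere cannot make this text a plan.

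**Conclusion.** Wrong as written. The section is a statistical analysis report under the heading of a plan, and no prespecification of tests, error level, primary analysis or cut-off rule is documented. Its p-values and cut-offs cannot be presented as prespecified or confirmatory. The general questions in the introductory part can fairly be called planned; the specific tests, p-values and cut-offs cannot.

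The size is a change in the kind of evidence, from confirmatory to exploratory. No corrected error rate can be derived from the documents. The illustrated overstatement of the Youden index depends on assumed distributions and on the cut-offs having been fitted to this sample, and the conclusion does not need it. The conclusion would change if a plan dated before data access were produced, for whatever that plan covers.

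**What to change.** - File any analysis plan dated before access to the data, and mark which analyses it covers.
- If there is none, retitle the section 'Statistical analysis report'. State in sections E, F and G that no prespecification is documented and that all p-values are exploratory.
- Present the IFS and TFS cut-offs as proposed for evaluation in an independent sample. If they were in fact fixed beforehand, say so and document it.
- Do not try to repair the gap by naming a primary estimate now; that choice would itself be post hoc.

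Without an earlier plan, these are changes of wording that need no new data or analysis; evaluating the cut-offs in an independent sample would be separate, later work. The downside is a weaker, exploratory claim.
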